7.1.2.4 Pregnancies

Testing for pregnancy for a female study subject with childbearing potential must be conducted at screening (or within 7 days of dosing). In addition, a urine pregnancy test will be performed prior to dosing on treatment day. Subjects who are pregnant or intend to become pregnant during the study will be excluded. Should a pregnancy occur with a study subject, the pregnancy should be reported to MediBeacon within 24 hours of the site's knowledge. All pregnancies will be followed to term, delivery or premature termination.

7.1.2.5 Device Observations / Malfunctions

All device observations, malfunctions or failures of the MediBeacon[®] Transdermal GFR Measurement System will be documented in the eCRF. In addition, failures of the sensor adhesive will be specifically documented.

7.1.2.5.1 Sensor Displacement

Prior dosing with MB-102:

Should a sensor be accidently removed (or significantly bumped) prior to receipt of MB-102, it should be removed from the subject, a new sensor placed on the subject, and baseline measurements re-started.

After dosing with MB-102:

If a sensor is accidently removed (or significantly bumped) following receipt of MB-102 but before a tGFR is calculated, the subject will remain in the study for safety follow-ups only for the full duration required by their stratum (12 hours or 24 hours). PK sample collection and fluorescent measurements will be terminated, however safety assessments (vital signs, ECGs and clinical safety labs) will be performed.

7.1.2.6 Clinical Laboratory Evaluation

Clinical laboratory assessments (**Table 3**) will be performed by a central lab in the US. A central lab will be used in China, if available. If the central lab is unavailable due to COVID-19, Chinese sites may utilize their local hospital laboratory if appropriately accredited. Reference ranges will be used by the investigator to assess the laboratory data for clinical significance and changes relative to baseline measurements. Clinically significant changes in laboratory values will be documented as adverse events.

Table 3 Clinical Laboratory Analytes

7.1.2.7 Vital Signs

Vital signs (including blood pressure, heart rate, respiration, and temperature) will be measured at screening, at multiple timepoints on dosing day(s), and at the follow-up visit. Vital signs should be collected while the subject is in a seated position and after resting for approximately 5 minutes for all measurements. Temperature is only collected at screening, pre-dose, and the completion of the dosing day, and at the follow-up visit.

7.1.2.8 Physical Examinations or Limited Physical Assessments

Physical examinations (when conducted by a physician, or other medically qualified investigator) or limited physical assessments (when performed by a nurse or other qualified individual) should include at a minimum an assessment of the head, ears, eyes, nose, throat (HEENT), respiratory, cardiovascular, and gastrointestinal systems. It is preferred that the same medical professional perform the baseline and post dosing assessments. Significant findings that were present prior to dosing must be included in the Medical History eCRF page. Significant new findings that begin or worsen after dosing must be recorded on the AE page of the eCRF.

Clinically significant abnormalities occurring post-dose should be evaluated by a physician and noted as AEs.

The study investigator will assess the subject for the occurrence of clinically significant new findings that begin or worsen after dosing which must be recorded as an AE on the eCRF page. A full physical exam should be conducted at screening and limited physical assessments may be conducted at other time points and must also be inclusive of the relevant organ or body system of interest for assessing the AE

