3.3 Clinical Data

A total of 266 subjects have been treated with an IV administration of MB-102 across the three pilot studies (Pilot 1A, Pilot 1B and Pilot 2 Groups 1, 2 and 3). The Pilot 1 studies enrolled subjects with an eGFR indicating normal renal function. The Pilot 2 study enrolled subjects with normal renal function and those with renal function in the CKD stage 1-5 range. In addition, a total of 22 subjects (11 healthy volunteers and 11 Crohn's patients) have received a 4 or 8 µmol/kg oral dose of MB-102 in a study evaluating the use of MB-102 in the evaluation of gut permeability (MediBeacon Protocol 300-01). The total population exposure to MB-102 as of this protocol is 288 subjects. A total of 52 subjects (18.1% of the total population across 4 studies) were reported to have adverse events (AE). All reported events were mild or moderate in severity. No severe events have been reported, nor have any serious adverse events been reported or unanticipated adverse device effects.

There have been no clinically significant findings with regard to vital signs, physical exams or ECGs. Overall MB-102 administered intravenously at a dose of 4 μ mol/kg whether or not followed by a 5 mL (milliliter) dose of iohexol (OmnipaqueTM 300), or at a fixed dose of 130 mg

/ 7 mL (n=44) or consumed orally at a dose of 4 μ mol/kg (n=8) or 8 μ mol/kg (n=14) was well tolerated in the populations studied to date.

Adverse events related to the device itself were due to the adhesive materials used to hold the ORFM (Optical Renal Function Monitor) sensor in place. All device related events were considered mild or moderate in severity. For more information, please see the Investigator's Brochure.

MB-102 equilibrates between the vasculature and tissues post IV administration. The plasma pharmacokinetics show a peak concentration at the first sample time point. In Pilot 1A and Pilot 2, the first sample time point taken was approximately 5 minutes post administration; in Pilot 1B the first sample time point taken was approximately 30 minutes post administration. The fluorescence pharmacokinetics, reflecting the agent concentration in the tissue, has a peak fluorescence intensity in the range of 30 - 90 minutes, depending on the subject. MB-102 concentration equilibration between the vasculature and the tissue occurs approximately 30 - 60 minutes after the peak.

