3.4 Study Rationale

This clinical study will evaluate the use of MB-102 and the MediBeacon[®] Transdermal GFR Measurement System for the purpose of marketing application with the final device design.

4 Study Objectives

The objectives of this pivotal study are:

- To establish that the MB-102 transdermal fluorescence measured GFR using the MediBeacon[®] Transdermal GFR Measurement System is comparable to the measured MB-102 plasma GFR
- To evaluate the safety and tolerability of a single dose of MB-102 in subjects
- To evaluate the safety and effectiveness of the MediBeacon[®] Transdermal GFR Measurement System for the non-invasive transdermal fluorescence detection of MB-102 in subjects

5 Investigational Plan

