6.1 Schedule of Assessments and Procedures

The schedule of planned study assessments is shown in **Table 2**.

Table 2 Study Schedule of Events

| Period | Pre-Screen (optional) | Screening | Dosing Day | Dosing Day | Dosing Day | Dosing Day | Follow-up Visit |
|--|--------------------------|--------------------------------------|------------|--------------------|--|--|-------------------|
| | | 21 days to day -2 prior to Dosing | Pre-dose | Dosing (time 0) | During 12 – 24 hours post IP injection | Completion of 12 hours or up to 24 hours post IP injection | 7 days +/- 3 days |
| Informed Consent ^a | Х | Х | | | | | |
| Inclusion / Exclusion | | Х | Х | | | | |
| Demographics | | Х | | | | | |
| Medical History | | Х | Х | | | | |
| Pregnancy Test for WOCBP ^b | | Х | Х | | | | |
| PE or Limited PA ^c | | Х | Х | | | | Х |
| Vital Signs ^d | | Х | Х | | Х | Х | Х |
| Height and Weight ^e | | Х | Х | | | | |
| Clinical Labs ^f | | Х | Х | | | Х | Х |
| Mexameter measurements | | | Х | | | | |
| Transdermal Data Collection ^g | | | Х | Х | Х | Х | |
| Drink water ^h | | | Х | Х | | | |
| Administration of MB-102 ⁱ | | | | Х | | | |
| PK blood collection ^j | | | Х | | Х | Х | |
| ECG ^k | | Х | Х | | | Х | |
| Concomitant Therapies ¹ | | Х | Х | | Х | Х | Х |
| Adverse Events ^m | | | Х | Х | Х | Х | Х |
| Document Fitzpatrick Skin Color Type ⁿ | Х | Х | | | | | |

Table 2 Legend

- a. Pre-screening consent may be used to evaluate skin color only. Full informed consent is required prior to any study related procedures being conducted.
- b. Negative pregnancy serum human chorionic gonadotropin (hCG) test at screening for women of childbearing potential (WOCBP) is required for eligibility. On dosing day, a urine pregnancy test will be conducted for WOCBP who agree to use an acceptable method of birth control
- c. A full physical examination (PE) is required at the screening visit. A full PE or limited physical assessment (PA) may be conducted prior to dosing. (Limited PA includes assessments of HEENT, respiratory, cardiovascular, abdominal systems). A full or limited exam may be conducted at the follow-up visit.

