6.7.1 Stratum 1 (12 hour follow-up)

During the course of the study day, it is particularly important for site teams to check the patency of PK catheters. If a catheter is determined to be compromised in anyway, another catheter may be placed in the same arm as the original catheter utilizing a different vein.

PK draws will be drawn via the venous catheter at the following timepoints:

- PK draw in K_2 EDTA tube at 5 minutes (±2 minute)
- PK draw in K_2 EDTA tube at 15 minutes (±2 minute)
- PK draw in K_2 EDTA tube at 30 minutes (± 2 minutes)
- PK draw in K_2 EDTA tube at 60 minutes (±2 minutes)
- PK draw in K_2 EDTA tube at 90 minutes (±2 minute)
- Vital sign collection at 90 minutes (±5 minutes)
- PK draw in K₂ EDTA tube at 120 minutes (±5 minutes)
- PK draw in K_2 EDTA tube at 180 minutes (±5 minutes)
- PK draw in K₂ EDTA tube at 240 minutes (±5 minutes)
- Vital sign collection at 250 minutes (±5 minutes)
- PK draw in K₂ EDTA tube at 300 minutes (±5 minutes)
- PK draw in K_2 EDTA tube at 360 minutes (±5 minutes)
- PK draw in K_2 EDTA tube at 480 minutes (±5 minutes)
- Vital sign collection at 500 minutes (±5 minutes)
- PK draw in K_2 EDTA tube at 600 minutes (±5 minutes)
- Perform a 12 lead ECG at 700 minutes (±5 minutes)
- Vital sign collection (includes temperature) at 710 minutes (±5 minutes)
- PK draw in K₂ EDTA tube at 720 minutes (±5 minutes)

- Obtain laboratory tests including chemistry, hematology, and urinalysis (See Section 7.1.2.6 and Table 3) at 725 minutes (±5 minutes)
- At the conclusion of TGFR measurements (when tGFR is reported on the monitor), the sensor may be removed
- Adverse events will be collected based on subject reports and medical team observations

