8.1 Investigational Drug

Clinical data from the Pilot 1A and 1B studies (total n = 32 subjects) included the following adverse events:

- Pilot 1A (n = 16)
 - Vasovagal reaction (1 subject)
 - Dizziness (1 subject, 2 events)

These events occurred in fasting subjects shortly after dosing and resolved on that day. No other AEs, injection site reactions, clinically significant laboratory values or significant changes in vital signs were noted during this study.

- Pilot 1B (n = 16)
 - Headaches (56.3% of subjects)
 - Erythema (at the site of the adhesive) (100% of subjects)
 - Diarrhoea (1 subject)
 - Dizziness (occurring in 1 subject following release from the study center)

Erythema was thought to be related to the adhesive used to adhere the sensor to the skin. Headaches were deemed related to the head strap required to hold the forehead sensor in place. Sensor placement on forehead was discontinued post Pilot 1B.

MB-102 is excreted in the urine. Therefore, urine discoloration (chromaturia) is expected but has not been considered an adverse event in prior studies.

In the Pilot 2 study, a total of 234 subjects with normal to compromised renal function have been exposed to MB-102. A total of 120 subjects received a dose of 4 μ mol/kg followed by a 5 mL injection of iohexol. Seventy (70) subjects received a single dose only (no iohexol) of 4 μ mol/kg of MB-102) and 44 have received a fixed dose of 130 mg (7 mL). All reported AEs were mild or moderate in severity and resolved without sequalae. Overall, MB-102 given in conjunction with or without iohexol was well tolerated in this subject population.

A total of 40 adverse events were reported in 28 treated subjects in Groups 1, 2 and 3 for an AE rate of 12.0% in the treated population. A total of 31 events were considered mild and 9 moderate events occurred in 5 subjects (2.5% of the population). There were no severe events

reported. There were no Serious Adverse Events (SAEs) reported during the study. There were no Unanticipated Adverse Device Effects (UADEs) reported during the study.

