8.2 MediBeacon[®] Transdermal GFR Measurement System

There are no direct risks associated with the MediBeacon[®] Transdermal GFR Measurement System (monitor portion) as it does not contact the study subject. Adverse events observed from the sensors are with regard to the methods used to affix it to the study subject. Risks may include a reaction to the sensor or adhesive material or the adhesive used on the skin clip.

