9.6 Safety Analyses

Safety of MB-102 will be evaluated through treatment emergent adverse events (TEAEs), where treatment emergence is defined with respect to the first dose of MB-102.

Safety of the MediBeacon[®] Transdermal GFR Measurement System will be evaluated through TEAEs, where treatment emergence is defined with respect to the start time of Transdermal GFR Measurement System use (placement of the sensor on the skin).

Additional safety variables include physical examinations, clinical laboratory assessments, ECGs, and concomitant medication use.

All safety analyses will be done for subjects receiving a single dose of MB-102.

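### The protocol requires no standardised inspection of the sensor site at removal or follow-up, so mild adhesive reactions may be under-counted or recorded unevenly

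*Combined protocol and SAP*

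**What the plan says.** Section 4 lists as an objective: "To evaluate the safety and effectiveness of the MediBeacon[®] Transdermal GFR Measurement System for the non-invasive transdermal fluorescence detection of MB-102 in subjects". Section 9.6 evaluates device safety through TEAEs counted from placement of the sensor.

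The protocol says what kind of device event to expect. On earlier studies, Section 3.3 states: "Adverse events related to the device itself were due to the adhesive materials used to hold the ORFM" sensor in place. Section 8.2 states: "Adverse events observed from the sensors are with regard to the methods used to affix it to the study subject". Section 8.2.1 adds redness, itching and other local skin reactions to the clip adhesive.

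Table 2 schedules a physical examination or limited assessment at screening, pre-dose and follow-up. Section 7.1.2.8 sets the content of either: it "should include at a minimum an assessment of the head, ears, eyes, nose, throat (HEENT), respiratory, cardiovascular, and gastrointestinal systems". Table 2 note c agrees: "Limited PA includes assessments of HEENT, respiratory, cardiovascular, abdominal systems". For dosing day, Section 6.7.1 says: "Adverse events will be collected based on subject reports and medical team observations", and Section 6.8 says the same for Stratum 2.

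**The concern.** The protocol measures device safety through adverse events and identifies one place on the body where a device event is most likely. Its examinations are not directed at that place. If nobody is required to look at the skin when the sensor comes off, a mild reaction enters the data only if the subject mentions it or a staff member notices it and judges it worth recording. Sites can differ in that habit, and a low reported rate could then reflect a well-tolerated adhesive, limited looking, or both. The trial supports a marketing application with the final device design (Section 3.4), so its skin-reaction rate is the one likely to be quoted.

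**Working it through.** The plan gives no figure for device-event ascertainment to reproduce. Its only design calculation is the sample size of 102 for P30 (Section 9.7). That reproduces with the exact binomial test: at least 94 successes in 102 gives a one-sided type I error of 0.0231 at 85% and power of 0.930 at 95%. Nothing below changes it.

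The check is a reading of each point at which the sensor site could be inspected:

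- **Pre-dose (6.3, 6.5, 7.1.2.11; exclusion 8).** The upper chest is examined for Fitzpatrick type, scarring, tattoos and pigment change at the sensor area are judged for eligibility, Mexameter melanin is read near the sensor location, and irritation from clipping is noted as medical history. The site is looked at, but there is no present/absent record of a skin reaction.
- **Sensor removal (6.7.1, 6.8, Table 2 note g).** Removal is allowed once a tGFR is reported, which may be before PK sampling ends. No skin check is attached.
- **Early dislodgement (5.5.1, 7.1.2.5.1).** The assessments listed are laboratory tests, vital signs and ECG. Skin is not among them, although the attachment has failed or been disturbed.
- **Device observations (7.1.2.5).** Adhesive failures are documented; the condition of the skin is not mentioned.
- **Follow-up (6.9).** A full or limited examination is done, with the 7.1.2.8 minimum. The sensor site is not named.
- **Extra body systems (7.1.2.8).** Another relevant system must be included when an adverse event is being assessed, so this clause follows up a known reaction rather than finding one.
- **Recording (7.1.2.8, 9.6.2).** Significant new findings go on the AE page, and examination data are not listed, so a finding not recorded as an adverse event cannot be recovered later.

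The injection site is treated differently: Section 6.6 requires it to be observed for named signs of infiltration.

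Timing matters. Section 8.1 reports two Pilot 2 discolorations at the sensor location that resolved within 24 hours of removal. Taking the longest wear stated in Section 5.5 (24 hours), such an event would be gone by about 24 + 24 = 48 hours. The nominal follow-up window opens at 7 − 3 = 4 days, or 96 hours. A skin check at follow-up alone would miss it; a check at removal would not.

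On size, the reported rate equals the true site-reaction rate multiplied by the proportion captured. The documents give neither factor for this trial, so no estimate can be formed.

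**The case against.** Adverse-event collection is not left to chance. Table 2 schedules it at pre-dose, dosing, during the sampling period, at its completion and at follow-up, starting from sensor placement. Dosing-day sources include staff observation as well as subject reports. Section 7.1.2.8 gives the investigator a general duty to look for clinically significant new findings after dosing, whether or not an event is already known. The examination list is a minimum, and a full examination is allowed at follow-up. Once reported, a reaction is followed until resolved or stable (7.1.2.1). Earlier device events were all mild or moderate (3.3), and device safety carries no hypothesis or threshold. The Study Procedure Manual, not among the documents, may contain a site check.

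Most of this stands, and it rules out the inference that the device adverse-event rate rests only on incidental reports. What remains is narrower: none of these provisions names the sensor site or fixes when it is looked at, and the general duty covers clinically significant findings rather than mild ones.

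Three other inferences should also be set aside:

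- **No record of the site before attachment.** The Fitzpatrick, exclusion 8 and Mexameter steps contradict this.
- **The pilots demonstrate under-ascertainment.** Section 8.1 gives adhesive-site erythema in 100% of 16 subjects in Pilot 1B, against device-related events in 7 of 234 in Pilot 2 (7/234 = 3.0%). The two figures count different things, Pilot 1B used a forehead sensor that was later discontinued, and neither account says how the skin was inspected. The gap is unexplained.
- **Redness is missed more often in darker skin.** Nothing in the documents addresses this.

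**Conclusion.** The point holds as a gap in ascertainment. The protocol text requires no standardised inspection of the sensor site at removal, after early dislodgement or at follow-up, although a skin reaction is the device risk it names. Mild or transient reactions may therefore be under-counted or unevenly recorded across sites. The check at removal matters most.

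The size cannot be estimated from the documents. The conclusion assumes that no binding instruction elsewhere, such as in the Study Procedure Manual, already requires the check. The consequence is limited to the descriptive device-safety results. The change is worth making, but the trial's main conclusion does not depend on it.

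**What to change.** Add one instruction and one eCRF item: inspect the sensor and clip site, and record whether a reaction is present and of what type. Place it:

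- at the existing skin preparation before attachment (6.5), as a present/absent note to complement the Fitzpatrick and Mexameter checks;
- at sensor removal in both strata (6.7.1, 6.8) and on the early-dislodgement paths (5.5.1, 7.1.2.5.1);
- as a required element of the follow-up examination (6.9, 7.1.2.8, Table 2 note c).

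Report the site-reaction rate by time point from these records, alongside the TEAE tables.

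The cost is one eCRF item at contacts where staff already handle or examine the subject, with no extra visit or device. The drawback is that the reported rate of mild skin events may rise, and comparisons with the pilot rates would need that caveat.

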7.1.2.9 ECGs

Standard 12 lead ECGs will be collected at screening, prior to dosing and at 700 minutes (±5 min). The following parameters will be assessed: interpretation, ventricular rate, PR interval, QRS duration, QT, and QTcF.

Subjects should be allowed to rest quietly approximately 10-15 minutes prior to their ECG. Additional ECGs may be collected if an issue or safety concern is noted.

An appropriately trained and experienced investigator will interpret the ECGs. A subject with an abnormal clinically significant ECG during screening does not qualify for the study. A subject with an abnormal not clinically significant ECG does not qualify for dosing without investigator comment on the ECG source document/eCRF.

7.1.2.10 PK Sample Collection

PK samples will be collected at the timepoints noted in **Table 2.** Recommendations for venous access and sample processing information are available in the Study Procedure Manual. PK samples should be collected in a manner to prevent haemolysis and placed on ice until processed and aliquoted into cryovials. PK samples must be stored frozen at -70 to -80°C until shipped for PK analysis.

7.1.2.11 Mexameter[®] Measurements

A commercially available Mexameter[®] device will be provided to the sites for the measurement of skin pigment (melanin) and erythema. The device should be used in accordance with the instructions provided in the Study Procedure Manual (including pre-use calibration). Measurements should be performed on subjects when they are not in close proximity to a window and should be made on the approximate location of sensor placement. It is advisable, when required, to clip excess hair as early in the dosing day as possible to allow transient redness due to the clipping process to fade. The site should note any skin irritation due to clipping as medical history. Mexameter[®] measurements of melanin will be collected prior to sensor placement.

